#### Administration of bowel function-related surveys:

- 1. Validated questionnaires related to bowel function and pain scores will be administered at two time points:
  - (a) At the patient's preoperative visit
  - (b) At their routine 2 week postoperative visit, they will submit their 5-day bowel diary. The primary outcome measures will also be gathered via telephone call to occur 1 week after surgery. At this visit, they will also complete a validated questionnaire regarding bowel function.

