#### **10. Study Endpoints\***

The primary outcome is the time to first bowel movement among those who receive preoperative fiber supplementation and those who do not.

The secondary outcome is pain associated with first bowel movement.

We also plan to perform an interval analysis after 50% of subjects have completed their surgery to evaluate postoperative bowel function. If a statistically significant difference (p<0.01) is found on this analysis, we will terminate the study.

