#### **11. PROCEDURES INVOLVED\***

#### Study design and randomization

This study is a randomized trial. We were unable to find a suitable placebo that had the same properties as the psyllium fiber supplementation, and thus we will compare psyllium fiber supplementation to our standard of care, which is no bowel regimen before surgery. Both groups will receive the routine postoperative bowel regimen offered to all patients on the urogynecology service.

Subjects will be screened for eligibility using inclusion and exclusion criteria in our urogynecology clinic after prolapse surgery has been scheduled. Once a patient provides informed consent for the surgical procedure, she will be invited to participate in this study. Once the subject has consented to participate in the study, baseline data will be gathered. Study assignment will be revealed using sequentially numbered sealed opaque envelopes. Randomization will be performed using software and a block randomization scheme to yield a 50% chance of receiving the preoperative fiber supplementation. Those assigned to the intervention group will receive a 7-day supply of fiber supplementation to be taken before surgery. The fiber will be procured, distributed and managed by the investigational drug pharmacy.

Neither the patient nor the provider will be blinded to the allocation of groups. However, our statistician will be blinded to allocation for the data analysis

Psyllium fiber is a commonly used and naturally occurring dietary supplement that is FDA-approved. It is available over-the-counter.

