#### **Postoperative care:**

Subjects will undergo routine postoperative care as inpatients and outpatients and have routine follow-up, including a postoperative evaluation at 2 and 6 weeks. Information on any postoperative complications will also be collected, such as severe constipation, infection, urinary tract infection. During our routine 1 week follow up phone call that all patients get, data regarding the primary outcome will be collected. At their 2 week postoperative visit, they will be asked to fill out a validated questionnaire regarding bowel function.

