#### **12. DATA AND SPECIMEN BANKING\***

#### N/A

#### 13. Data Analysis and Management\*

Previous studies have found that the average time to first bowel movement ranges between 64 hours – 81 hours. Our quality data finds time to first bowel movement averaging approximately 72 hours. Most studies have targeted a 24 hour decrease in time to first bowel movement. We plan to target a similar difference as we feel this is a clinically significant difference in the patient's postoperative recovery period. Using a Pearson chi-squared test with a significance level of 5% and power of 80%, this yields 35 patients per arm (70 patients total). Assuming a 20% drop-out rate, we seek to recruit 84 patients.

Continuous measures will be compared using the Student's t-test. Standard statistical programs (SAS, SPSS, and STATA) will be used to perform these tests.

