#### 14. PROVISIONS TO MONITOR THE DATA TO ENSURE THE SAFETY OF SUBJECTS\*

Psyllium fiber is a natural-occurring dietary supplement that is available over the counter and is commonly used across millions of individuals in the United States. It comes in insoluble and soluble forms, both of which are important for a balanced diet. We plan to use psyllium in a powdered form, which contains 70% soluble fiber and 30% insoluble fiber. The normal recommended dose for fiber in the form of powdered psyllium is 1 teaspoon up to three times daily. We plan to prescribe 1 teaspoon twice daily in the form of powdered, pre-measured packets that are to be mixed with 8 oz of water or other cool liquid. We will obtain the psyllium fiber through wholesale distribution that has been determined by the investigational drug pharmacy. Receipt, storage, preparation, accountability, dispensing and return/destruction of all study drug will be performed by the Investigational Drug Service (IDS) at the Memorial Campus Inpatient Pharmacy. The Investigational pharmacy has been contacted regarding this study and has received the study protocol and package insert.

The IDS will verify that study drugs supplies are received intact, at the appropriate temperatures, and in the correct amounts from the study drug supplier.

Study drug will be dispensed only by prescription. Research staff will transfer the prepared study medication from the pharmacy to the Urogynecology clinic on West 4th floor of UMass Memorial to give to the subject. The study drug will not be used for reasons other than that described in the protocol. Attached to this protocol is an informational sheet regarding fiber supplementation.

Psyllium fiber supplement is generally well tolerated. It can cause bloating and abdominal discomfort. Subjects will be advised to stop the fiber if they develop symptoms such as abdominal pain, nausea or vomiting. All subjects will have access to our office and an on-call physician should any medication side effects or adverse reactions develop.

If any adverse event were to arise, they would be evaluated by the on-call physician.

We will do an interval analysis of the primary outcome once 50% of subjects have completed the

study. If a statistically significant difference (p<0.01) is found in favor of psyllium fiber supplementation, we will terminate the study and offer preoperative psyllium fiber supplementation to all our patients.

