#### **22.** Setting

Subjects will be identified and recruited in the urogynecology clinic at UMass Memorial on West 4th floor at the time of their pre-operative visit. At this visit, the patients will be consented, and they will also fill out the pre-operative questionnaire. At this time, they will also be randomized

to standard of care versus intervention. The urogynecology division has two full-time designated surgeons (including the PI) and both will participate in the study. In addition, the department fellows and nurse practitioner will work as co-PI and study assistants. This comprises the team who will recruit subjects and obtain intraoperative and postoperative study data.

Data entry and analysis will be performed in the administrative offices of the division on Jaquith 2 in UMass Memorial.

There will be no community advisory board, and this research will not be conducted outside of UMass or its affiliates.

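### A preoperative bowel-function score is collected, but the primary comparison is unadjusted; pre-specified adjustment for one named score would be a cheap, optional efficiency gain

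*Combined protocol and SAP*

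**What the plan says.** **Baseline collection.** Section 11 (Administration of bowel function-related surveys) states "Validated questionnaires related to bowel function and pain scores will be administered at two time points": the preoperative visit and the 2-week visit. Section 22 adds "At this visit, the patients will be consented, and they will also fill out the pre-operative questionnaire", and then says that randomisation takes place at that time. Section 11 (Study design and randomization) gives the order after consent: "baseline data will be gathered. Study assignment will be revealed using sequentially numbered sealed opaque envelopes".

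**Analysis.** Section 13 gives one sentence on the comparison: "Continuous measures will be compared using the Student's t-test". The text mentions no covariate, regression model, stratification or other use of the preoperative questionnaire.

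**Size.** Section 13 derives 35 per arm from a 24-hour difference, 5% significance and 80% power, then says "Assuming a 20% drop-out rate, we seek to recruit 84 patients".

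**Interim.** Section 10 plans a look at half the subjects with a p<0.01 stopping threshold. Section 14 makes clear which outcome is meant: "We will do an interval analysis of the primary outcome once 50% of subjects have completed the" study.

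**Pain.** It is unclear whether a preoperative pain score exists. The opening line on the surveys mentions pain scores. For the 2-week visit, section 11 (Postoperative care) says only "they will be asked to fill out a validated questionnaire regarding bowel function", and section 22 refers to a single preoperative questionnaire.

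**The concern.** The trial is small, and it collects a measurement that may predict how soon bowel function returns. If a baseline score is related to the outcome, including it in the model removes the part of the variance that it explains and narrows the confidence interval for the difference in hours, with no extra subjects or data. The plan leaves this unused.

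At stake is precision, not validity. The potential gain is limited from the start: time to first bowel movement after surgery has no baseline value, so the questionnaire score is only a proxy for it.

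**Working it through.** **1. The plan's own figure.** The 35 per arm cannot be reproduced from stated inputs. The chi-squared test named for the sample size needs two proportions and a t-test needs an SD; neither is given. I therefore back-solved the SD that makes 35 per arm correct for a two-sided 5% t-test with 80% power and a 24 h difference:

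- Normal approximation: SD = 24 × √(35/2) / (1.960 + 0.842) = 35.8 h.
- Noncentral t, 68 df: standardised difference 0.679, so SD = 24/0.679 = 35.3 h.

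I use 35.3 h. It is an assumption, as is two-sided testing.

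**2. Sample sizes.** Final analysis: 35 per arm as planned, or 84 × 0.8 / 2 = 33.6 per arm if 20% of those recruited are lost. Interim: 50% of 84 = 42, or 21 per arm with no loss.

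**3. Formulas.** With n per arm, N = 2n and correlation ρ between score and outcome:

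- Unadjusted: variance of the difference = SD² × 2/n, df = N − 2.
- Adjusted for one covariate: variance = SD² × (2/n) × (1 − ρ²) × (1 + 1/(N − 4)), df = N − 3.

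The last factor is the average cost of chance imbalance in the covariate: 1 + 1/66 = 1.0152 at 35 per arm, 1.0158 at 33.6 and 1.026 at 21. Power is from the noncentral t distribution.

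**4. Worked line, ρ = 0.3, 35 per arm.** Unadjusted SE = 35.33 × √(2/35) = 8.44 h. Adjusted SE = 35.33 × √((2/35) × 0.91 × 1.0152) = 8.12 h. Power rises from 80.0% to 83.0%.

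**5. Results for a true difference of 24 h.**

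| Correlation | SE, 35 per arm | Final power, 35 per arm | Final power, 33.6 per arm | Interim power, 21 per arm, p<0.01 |
|---|---|---|---|---|
| Unadjusted | 8.44 h | 80.0% | 78.3% | 32.1% |
| 0 | 8.51 h | 79.4% | 77.7% | 31.0% |
| 0.1 | 8.47 h | 79.8% | 78.1% | 31.4% |
| 0.2 | 8.34 h | 81.0% | 79.3% | 32.6% |
| 0.3 | 8.12 h | 83.0% | 81.4% | 34.7% |
| 0.4 | 7.80 h | 85.8% | 84.4% | 38.0% |
| 0.5 | 7.37 h | 89.4% | 88.1% | 43.1% |

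**6. Break-even.** Adjusted and unadjusted power are equal at ρ = 0.124 (35 per arm), 0.127 (33.6 per arm) and 0.167 (interim).

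**7. Sensitivity to the SD, 33.6 per arm, ρ from 0 to 0.5.** SD 30 h: 89.8% unadjusted, 89.3% to 95.9% adjusted. SD 40 h: 67.8% unadjusted, 67.1% to 79.3% adjusted. The pattern is the same: a small loss at zero correlation and a gain that depends on a value nobody has stated.

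**8. Why one score, named in advance.** In a null simulation (10,000 runs, 35 per arm, four candidate scores), one pre-specified score kept the type I error near 5%. Taking the smallest p-value from the four adjusted tests and the unadjusted test raised it to 7.3% (ρ = 0.3) and 9.1% (ρ = 0.5).

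**The case against.** The strongest reply is that nothing in the plan is wrong. An unadjusted comparison of randomised groups is legitimate, and the benefit rests on a correlation that the documents do not give, with a proxy score from an unnamed instrument. At a correlation of 0.1 adjustment loses slightly; at 0.2 it gains 1 point of final power. Gains of 6 to 9 points need 0.4 to 0.5, for which the documents offer no support. All of this stands, and it is why the point is an option to consider.

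A reader might also infer that the stopping decision is already ambiguous, because section 10 says only "We also plan to perform an interval analysis after 50% of subjects have completed their surgery to evaluate postoperative bowel function" and names no test. In simulated interim data with a true 24 h difference, adjusted and unadjusted tests would disagree on stopping in 4.0% to 18.2% of trials over correlations 0 to 0.5. The documents do not support that reading as a defect. Section 14 says the look is at the primary outcome and section 13 gives one test for continuous measures, so together they imply the t-test at both looks. The conflict arises only once an adjusted model is considered.

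Two further reservations stand in part. Section 11 does not say outright that the questionnaire belongs to the baseline data gathered before the envelope is opened; the order in section 22 makes it likely. A linear model on hours also shares with the t-test any difficulty from skewed or censored times, so the choice of primary analysis scale comes first.

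**Conclusion.** The point holds as a cheap efficiency improvement. A baseline bowel-function score is collected, apparently before assignment is known, and the stated analysis does not use it. It would be wrong to conclude that the unadjusted analysis is invalid or biased: randomisation justifies the t-test.

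No particular gain can be promised. Under the assumed SD of 35.3 h and 35 per arm, the change in final power runs from −0.6 points (correlation 0) through +3.0 (0.3) to +9.4 (0.5). The trade is favourable if the authors have reason to expect a correlation above about 0.12 at the final analysis, or about 0.17 for a gain at the interim too. The proposal does not resolve the mismatch between the chi-squared test used for sample size and the t-test named for analysis.

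**What to change.** In section 13:

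- Pre-specify the primary comparison as a linear model (ANCOVA) of time to first bowel movement on treatment, adjusted for one named preoperative bowel-function score completed before the envelope is opened.
- Fill a missing baseline score with the mean over both arms, so that no randomised subject is lost for that reason.
- Keep the unadjusted t-test as a sensitivity analysis.
- Because the model replaces the t-test, state that the p<0.01 look at 50% uses the same adjusted model. This condition comes with adopting the change.
- Do not adjust for the last bowel movement or adherence recorded on the day of surgery (section 11, Surgery); both come after randomisation.
- Adjust pain at first bowel movement for preoperative pain only if a defined preoperative pain score is in fact collected.
- If a time-to-event analysis is adopted instead, use the same baseline covariate there, and note that adjustment changes the hazard ratio being estimated.

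The cost is a short paragraph and one degree of freedom, with no new data field provided the questionnaire yields a usable single score. If that score is not prognostic, power falls from 80.0% to 79.4% at the final analysis (78.3% to 77.7% after 20% loss) and from 32.1% to 31.0% at the interim.

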#### **12. DATA AND SPECIMEN BANKING\***

#### N/A

#### 13. Data Analysis and Management\*

Previous studies have found that the average time to first bowel movement ranges between 64 hours – 81 hours. Our quality data finds time to first bowel movement averaging approximately 72 hours. Most studies have targeted a 24 hour decrease in time to first bowel movement. We plan to target a similar difference as we feel this is a clinically significant difference in the patient's postoperative recovery period. Using a Pearson chi-squared test with a significance level of 5% and power of 80%, this yields 35 patients per arm (70 patients total). Assuming a 20% drop-out rate, we seek to recruit 84 patients.

Continuous measures will be compared using the Student's t-test. Standard statistical programs (SAS, SPSS, and STATA) will be used to perform these tests.

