# 8. Study-Wide Recruitment Methods\* N/A

#### 9. STUDY TIMELINES\*

Subjects will be enrolled from one week before their surgery until 6 weeks after surgery.

Our urogynecology department had approximately 90 postoperative admissions over 12 months (from October 2017 to October 2018). Given this trend, we anticipate approximately 20-24 months to recruit 84 patients.

Primary analysis will be completed within 6 months after enrollment is completed.

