#### 24. LOCAL RECRUITMENT METHODS

Our power calculation, as detailed previously in question 13, requires 70 total subjects (35 per

arm). Assuming a 20% drop-out rate, we seek to recruit 84 patients. Our urogynecology department had approximately 90 postoperative admissions over 12 months (from October 2017

to October 2018). Given this trend, we anticipate approximately 20-24 months to recruit 84 subjects for the study.

All subjects will be identified and recruited through the urogynecology clinic, at the clinic site previously mentioned in question 22, after prolapse surgery has been scheduled. Our two full time surgeons (including the PI) will both participate in the study, as well as the department fellows—therefore, this yields access to every surgical urogynecology patient. The study team will screen potential subjects using inclusion and exclusion criteria at their preoperative visit, since this routinely includes a review of the patient's medical history. No identifiers will be recorded during screening. Once eligibility has been determined, potential subjects will be offered to participate in the study by their surgeon only after surgical consent has been discussed and obtained for the patient's surgery. Clinical staff will not be involved in the recruitment process. The study will be reviewed in detail and ample opportunity for questions will be given. The opportunity to decline participation will also be given, and no information on these patients will be recorded for this study. An un-identified tally will be recorded counting screened patients who were "ineligible" or "declined". For women agreeing to participation, informed written consent will be obtained.

There will be no payment to subjects in the study.

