#### **25. LOCAL NUMBER OF SUBJECTS**

We seek to enroll 84 subjects in the study.

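### Recruiting 84 women at the plan's own 20% drop-out rate leaves about 67 evaluable, not the required 70; the inflation step multiplied by 1.20 instead of dividing by 0.80

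*Combined protocol and SAP*

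**What the plan says.** Section 13 derives the number needed and the recruitment target in consecutive sentences: "this yields 35 patients per arm (70 patients total). Assuming a 20% drop-out rate, we seek to recruit 84 patients". The basis given there for the 35 per arm is "Using a Pearson chi-squared test with a significance level of 5% and power of 80"%, aimed at a 24-hour reduction in time to first bowel movement.

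Section 24 (Local Recruitment Methods) repeats the calculation. The power calculation "requires 70 total subjects (35 per" arm), and then: "Assuming a 20% drop-out rate, we seek to recruit 84 patients".

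The resulting 84 is carried into two more places. Section 9 (Study Timelines) says "Given this trend, we anticipate approximately 20-24 months to recruit 84 patients", and section 25 (Local Number of Subjects) says "We seek to enroll 84 subjects in the study". Allocation is equal: section 11 describes "a block randomization scheme to yield a 50% chance of receiving the preoperative fiber supplementation".

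**The concern.** The plan states three linked figures: 70 women needed, 20% lost, 84 recruited. With the loss taken as a share of recruits, any two of them fix the third, and the three as written do not agree. The 84 matches 70 increased by one fifth. That would allow for losses equal to 20% of the women who finish, which is a smaller allowance than losing 20% of the women who start.

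The 70 is the only number the plan connects to 80% power, and section 13 states no margin above 35 per arm. If drop-out runs at the rate the plan assumes, the trial would therefore finish below its own requirement even with recruitment fully on target.

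**Working it through.** **Inputs**

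| Quantity | Value | Source |
|---|---|---|
| Women required | 70 (35 per arm) | Sections 13 and 24 |
| Drop-out rate | 20% | Sections 13 and 24 |
| Recruitment target | 84 | Sections 9, 13, 24 and 25 |
| Allocation | 1:1 | Section 11 |
| Recruitment time | 20 to 24 months | Sections 9 and 24 |

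**Step 1: reproduce the plan's figure.** With n = 70 and d = 0.20, n × (1 + d) = 70 × 1.20 = 84. This matches exactly. Per arm, 35 × 1.20 = 42.

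**Step 2: apply the stated drop-out to the stated target.** 84 × (1 − 0.20) = 67.2, or 33.6 per arm. The shortfall is 70 − 67.2 = 2.8, about 3 women.

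**Step 3: find the drop-out that 84 tolerates.** 1 − 70/84 = 14/84 = 16.7%.

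**Step 4: find the target that 20% drop-out requires.** n / (1 − d) = 70 / 0.80 = 87.5, rounded up to 88 (44 per arm). Check: 88 × 0.80 = 70.4. Rounding cannot turn 87.5 into 84.

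**Step 5: illustrate the power effect.** The plan gives neither a standard deviation nor proportions, so the effect sizes here are assumptions. Each was back-solved so that 35 per arm gives exactly 80% power at two-sided 5%. The plan does not state sidedness. For the t-test this means a standardised difference of 0.679, which for 24 hours implies a standard deviation of about 35.3 hours. For the chi-squared test, five assumed pairs of proportions were used: 0.10 v 0.38, 0.20 v 0.52, 0.30 v 0.63, 0.40 v 0.73 and 0.50 v 0.81.

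| Women per arm | t-test | Chi-squared |
|---|---|---|
| 35 / 35 | 80% | 80% |
| 34 / 34 | 78.8% | not computed |
| 33 / 34 | 78.2% | 78.1% to 78.2% |
| 33 / 33 | 77.6% | 77.6% |

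The loss is 80 − 78.8 = 1.2 points to 80 − 77.6 = 2.4 points, and where both tests were computed they agree.

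**Step 6: cost of 88 at the plan's own pace.** The pace is 84/24 = 3.5 to 84/20 = 4.2 women a month. Then 88/4.2 = 21.0 months and 88/3.5 = 25.1 months.

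**The case against.** The strongest reply accepts the arithmetic and disputes its weight.

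- **The effect is tiny.** Under the assumed t-test with 33 and 34 women, the difference detectable at 80% power moves from 24 hours to about 24.5 hours, and only if drop-out really reaches 20%. This stands: the point is not a serious power problem.
- **The base is uncertain.** Section 13 names a chi-squared test for a difference in hours, gives no proportions or standard deviation, and then plans t-tests for continuous measures. With 35 per arm, a 24-hour difference and assumed standard deviations of 30, 36 or 40 hours, power would be about 91%, 79% or 70%, a spread far wider than the loss at issue. This also stands, as a separate and larger problem. It does not excuse the inflation step, which would carry the same error onto any corrected base: the factor for 20% loss is 1/0.80 = 1.25, not 1.20.
- **The 20% is not defined.** Adding a fifth to the evaluable number is a common shorthand, and on that reading 84 is consistent. However, nothing visible in the plan defines the rate as a share of completers, and a drop-out rate stated beside a recruitment figure is naturally read as a share of recruits. That the sponsor multiplied by 1.20 is inferred from the exact match; the plan does not say so.
- **Real losses may be lower.** The primary outcome is collected in a routine one-week telephone call, supported by a five-day diary (section 11), so losses may stay within 14. That is possible, but it is an argument for stating a lower rate. The remark in section 15 that no removals are expected concerns withdrawal without consent, and section 30 lets women withdraw at any time.
- **A replacement rule might exist.** None appears in the visible text, but some parts of the document were removed before review, so one there cannot be excluded.

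**Conclusion.** The concern holds. With drop-out read as a share of women recruited, 70 required, 20% lost and 84 recruited cannot all be true. At the stated rate the trial expects 67.2 evaluable women (33 or 34 per arm), about 3 short, and 84 protects the 70 only up to 16.7% loss.

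The consequence is modest: roughly 1 to 2.5 points of power, conditional on 35 per arm giving 80% in the first place, which the documents do not let anyone verify. The shortfall in women needs no such assumption and follows directly from the plan's own figures. The statement should be corrected because it is wrong as written and costs almost nothing to put right, not because it threatens the trial.

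**What to change.** Any one of these makes the figures agree:

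1. **Keep 84 and restate the allowance** as 16.7% (14 of 84) in sections 13 and 24. This is the simplest change: one sentence in each section and no extra women. The cost is an openly smaller tolerance for loss.
2. **Keep 84 and 20%, and restate the expected yield.** Say in sections 13 and 24 that about 67 evaluable women are expected, with power slightly below 80%, recomputed from the sponsor's own inputs.
3. **Keep 70 and 20%, and raise the target to 88.** This adds 4 women and takes about 21 to 25 months instead of 20 to 24. Sections 9, 13, 24 and 25 need editing. If the 50% interim point in sections 10 and 14 refers to the enrolment target, it moves from 42 to 44.

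Before choosing option 3, the sponsor should settle the basis of the 35 per arm, since 88 is only as sound as the 70 behind it. If that base changes, the new number should be divided by one minus the drop-out rate. Whichever option is taken, the text should say that the rate is a share of women recruited.

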#### Surgery:

On the day of surgery, we will collect information from the patient about their last bowel movement as well as if they were able to adhere to the fiber regimen, had they been allocated to that group. Prolapse surgery will be performed in the usual manner. There will be no changes to the surgical technique for the purposes of the study.

Subjects will receive routine perioperative and postoperative care for their scheduled surgery. The study intervention will require postoperative data collection including the gathering of PHI, a 5-day bowel diary and recording of post-operative medications.

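### The 35 per arm rests on a chi-squared test with no proportions, while the planned t-test has no SD and no rule for a woman without a bowel movement by the 1-week call

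*Combined protocol and SAP*

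**What the plan says.** Section 10 defines the outcome as a time: "The primary outcome is the time to first bowel movement among those who receive preoperative fiber supplementation and those who do not". It gives no cut-off that would make it a yes/no outcome.

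Section 13 sets the effect in hours: "Our quality data finds time to first bowel movement averaging approximately 72 hours" and "Most studies have targeted a 24 hour decrease in time to first bowel movement", a target the trial adopts. It then sizes the trial with a test for proportions: "Using a Pearson chi-squared test with a significance level of 5% and power of 80%, this yields 35 patients per arm". The one sentence on analysis is "Continuous measures will be compared using the Student's t-test". No SD is given, only a range of published means (64 to 81 h). Section 24 carries the total forward: "Our power calculation, as detailed previously in question 13, requires 70 total subjects". The inflated total of 84 appears in Sections 9, 13, 24 and 25.

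Section 11 gives the data sources: "a 5-day bowel diary and recording of post-operative medications", a telephone call 1 week after surgery at which the primary outcome is collected, and a 2-week visit at which the diary is handed in and a bowel-function questionnaire completed. No section says what time is given to a woman who has had no movement by the call, or which source prevails.

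**The concern.** A chi-squared test compares two proportions and a t-test compares two means. They need different inputs and in general give different sample sizes for the same data. A size computed for one does not guarantee power for the other, so the stated 80% is not tied to the planned analysis.

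Separately, a t-test needs a number for every woman. A woman with no movement by the call has no observed time, only a lower bound. She could be left out, scored at the limit or followed further, and the plan does not choose. If fiber works, late movements are more common among controls, so leaving such women out would remove more long times from the control arm and understate the benefit. The halfway look (Sections 10 and 14, p<0.01) would depend on the same unwritten choice.

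**Working it through.** **Inputs from the documents.** Control mean 72 h, difference 24 h (so 48 h on fiber), alpha 5%, power 80%, 35 per arm, 1:1 allocation, call at 1 week (168 h). **Assumed, because not given:** two-sided test, the SD, and the shape of the distribution.

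**1. Can 35 be reproduced?** Not from the stated inputs: the chi-squared formula needs two proportions and the t-test formula needs an SD. It can only be solved backwards.

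- *As a comparison of means.* n = 2(1.960 + 0.842)² SD²/24². Setting n = 35 gives SD = 24 × √(35/2)/2.802 = 35.8 h. With the exact (noncentral) t distribution it is 35.3 h.
- *As a chi-squared test.* For 1/3 v 2/3 without continuity correction, n = [1.960√(2 × 0.5 × 0.5) + 0.842√(2/9 + 2/9)]²/(1/3)² = (1.386 + 0.561)² × 9 = 34.1, rounded up to 35 (40 with the correction). Nothing in the documents points to this pair.

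**2. How far does 35 depend on the SD?** Noncentral t, two-sided 5%:

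| SD (h) | Needed per arm for 80% |
|---|---|
| 24 | 17 |
| 28 | 23 |
| 35 | 35 |
| 42 | 50 |

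**3. Are the two tests interchangeable?** Take normal times with SD 35.8 h, so that 35 per arm gives the t-test 80%. Split at 60 h: the proportions with a movement are Φ((60 − 72)/35.8) = 0.369 and Φ((60 − 48)/35.8) = 0.631. The chi-squared test then needs 56 per arm, and 35 per arm gives 60% power. A split at 48 or 72 h needs 59 and gives 58%.

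**4. What does the missing rule do?** Let S = 35.33 h, the SD at which a t-test with 35 per arm has 80% power. Take either equal SDs, or SDs proportional to the mean (1.2S = 42.4 h control, 0.8S = 28.3 h fiber).

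Worked case, lognormal with proportional SDs. σ² = ln(1 + (SD/mean)²) = 0.298 and σ = 0.546 in both arms; μ = ln(mean) − σ²/2 = 4.128 and 3.722; z = (ln 168 − μ)/σ = 1.826 and 2.569.

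- No movement by 168 h: 1 − Φ(z) = 3.4% control, 0.5% fiber.
- Mean after leaving these women out: mean × Φ(z − σ)/Φ(z) = 72 × 0.900/0.966 = 67.1 h and 48 × 0.978/0.995 = 47.2 h. The difference is 19.9 h, not 24 h.
- Mean with times capped at 168 h: mean × Φ(z − σ) + 168 × [1 − Φ(z)] = 70.5 h and 47.8 h. The difference is 22.7 h.

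Simulated trials (40,000 per case, 35 per arm, gamma and lognormal times):

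| S = 35.33 h | Proportional SDs | Equal SDs |
|---|---|---|
| Trials with at least one woman unresolved at 168 h | 70–75% | 58–68% |
| Difference, left out | 19.9–20.2 h | 23.5 h |
| Difference, capped | 22.7–23.1 h | 23.9 h |
| Power, left out | 74–79% | 84–90% |
| Power, capped | 81–83% | 82–85% |
| Significance changes with the rule | about 9% of trials | 6–8% |

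At S = 24 h the left-out difference is 23.1–24.0 h and significance changes in at most 0.6% of trials. At S = 42 h it is 17.4–17.9 h (proportional) or 23.1 h (equal), and significance changes in 12–16%. With both means at 72 h, type I error is 4.7–5.2% under either rule.

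**The case against.** **The number may be right.** 35 per arm is what a t-test needs at an SD of about 35 h. This stands. A reader might infer that the trial is underpowered, but the documents give no SD and do not support that. They support only that the figure cannot be checked.

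**Nothing says women are left out.** This also stands. A reader might infer that the plan drops women without a movement. Section 13 is silent, and exclusion is one possible reading. The fault is the missing rule.

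**The bias may be small.** Correct with equal SDs, where even an SD of 42 h leaves 23.1 h of the 24 h. The loss to about 20 h needs an SD that scales with the mean. Nor does leaving women out raise the false-positive rate in these simulations.

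**Follow-up does not end at 168 h.** Women are seen again at 2 and 6 weeks, and severe constipation is recorded as a complication. A late first movement could be learned then. But Section 11 does not give the 2-week visit that task, and the diary covers only 5 days, so the visit is a way to repair the gap rather than a rule already in place.

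**Capping does not always gain power.** True: with equal SDs it loses some. The case for it is a rule fixed in advance and less bias.

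**Baseline adjustment.** Section 11 says "Once the subject has consented to participate in the study, baseline data will be gathered", and a preoperative bowel questionnaire is completed. Leaving it out of the analysis is not an error, because an unadjusted comparison of randomised arms is valid.

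**Conclusion.** The concern holds in two limited parts.

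First, the 35 per arm and its 80% power are not tied to the planned analysis. The test used for sizing does not match the outcome, the 24 h target or the named t-test, and neither test has the inputs it needs. If the sizing test were actually used on a split outcome, power would be about 60% under normal times with an SD near 35 h.

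Second, the t-test has no value for a woman without a movement by the call. How much this matters depends on an SD and a distribution that the documents do not give. It is negligible at 24 h. At about 35 h the benefit would be understated by about 4 h if the SD scales with the mean and by about 0.5 h with equal SDs, and in either case the choice of rule would change significance in roughly 6–9% of trials. These figures assume means of 72 and 48 h, gamma or lognormal times, 35 per arm with complete follow-up to 168 h, and a comparison of leaving women out with scoring them 168 h.

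This should be corrected. It does not show that the sample size is too small or that a positive result would be unreliable.

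**What to change.** In Section 13, replace the t-test sentence with one named primary analysis: the difference in mean time to first bowel movement, capped at 168 h, among randomised women by assigned arm. Add the rules:

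- Take the time from the diary, then from the 1-week call; use the 2-week visit to confirm women still unresolved at the call.
- Score 168 h only for women known to have had no movement by 168 h.
- Treat women last known without a movement before 168 h (for example, an early call) as censored, in a restricted-mean sensitivity analysis.
- Report by arm how many women have no source at all.

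In Sections 13 and 24, restate the sample size or power for this comparison of means with its SD, in place of the chi-squared test. Take the SD from the site quality data behind the 72 h mean if they hold it; otherwise show a range. If it exceeds about 35 h, restate the power for 35 per arm rather than enrol more. Keep the totals in Sections 9 and 25 consistent. Adjustment for the preoperative bowel score is optional: the instrument is not named, and the gain depends on an unknown correlation (at SD 35 h, a loss of 0.3 to 0.7 power points at correlation 0 and a gain of about 4 to 5 at 0.4).

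**Cost.** Wording and a standard procedure in the listed software. No new visit is needed, provided the call, and the 2-week visit for unresolved women, record when the first movement occurred. The estimate becomes a difference within 168 h (22.7–23.9 h rather than 24 h at SD 35 h). With equal SDs, power is about 2 to 6 points below a t-test that leaves unresolved women out (82–85% v 84–90% at SD 35 h; 71–78% v 75–84% at 42 h).
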